## **8 QUALITY CONTROL AND QUALITY ASSURANCE**

### **8.1 Data Safety Monitoring Board (DSMB)**

The Safety Committee of this trial will consist of three members of the scientific community not involved in this trial. The committee will meet quarterly (usually by phone conference) with the National Coordinating Investigator (LKP) of the trial and review all serious adverse events (SAE), suspected unexpected severe adverse reactions (SUSARS) and will be informed about statistically significant differences between the treatment arms. The Safety committee will give recommendations about the continuation of the trial and/or about necessary trial amendments.

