In order to ensure double blinding, the pharmacy will assign treatment arm A and B to Sorafenib or Placebo and neither the Studienzentrale SAL nor the investigators will know which treatment arm corresponds to Sorafenib and Placebo, respectively. The closed envelopes concealing the allocation of the individual patients will be deposited at the Dresden pharmacy and the local trial site only and not at the Studienzentrale. The Studienzentrale SAL will keep the randomization lists confidential and will not report the treatment arm to the investigators in order to ensure that in case of unblinding of one patient the investigator remains blinded for all other included and randomized patients. In case of unblinding, the investigators will have to contact the Safety Board which is separated from the randomization department at the Studienzentrale SAL. Even if the investigator reports the result of the unblinding to the Safety board, the results will not be reported to the randomization department. Therefore, in case of unblinding of an individual patient, the randomization department at SAL will still not be able to know which treatment arm corresponds with Placebo or Sorafenib and blinding throughout the whole trial period is guaranteed.

The centers will be supplied with starter medication kits after initiation of the study in the individual center. The center will report the eligible patient to the Studienzentrale SAL by faxing the patient registration form (Patientenmeldebogen) and send the required bone marrow and blood probes (Table 16, page 29) to the central laboratories (Table 17, page 29). After the Studienzentrale SAL has received the molecular and cytogenetic test results from the reference laboratories, the Studienzentrale SAL will perform the randomization as described above and

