## **6.2 Safety monitoring and reporting of AEs**

AEs and SAEs will be recorded from the time the informed consent is signed, up to and including 30 days following last administration of study drug.

Severity of adverse events and serious adverse events will be graded according to the National Cancer Institute Common Terminology Criteria for Adverse Events (CTCAE) 3.0 for Cancer Clinical Trials.

All adverse events have to be recorded on the appropriate adverse event pages in the CRF.

The National Coordinating Investigator (LKP) is responsible for central safety monitoring and reporting on behalf of the sponsor and has installed a central safety desk located at the Studienzentrale SAL. The investigator must fax all serious adverse events (SAEs) identified by the protocol as requiring immediate reporting on an SAE form to the safety desk within 1 working day.

This applies regardless of severity (CTCAE 3.0 grade) and whether or not the SAE is considered related to the use of study drug by the investigator. Where possible, a diagnosis rather than a list of symptoms should be given. The investigator should complete all the details requested including dates of onset, severity, corrective therapies given, outcome and opinion as to whether the adverse event is likely to be drug-related. The investigator should not wait for full details before making the initial report. Personal data have to be replaced by the trial patient number before forwarding any information.

If the event is fatal or life threatening, the investigator must fax any relevant follow-up information of the reported SAE to the safety desk within additional 8 days. If the reported SAE is not fatal or life threatening, the investigator must fax follow-up information as soon as possible.

Via the central safety desk, the National Coordinating Investigator (LKP) will review the SAE again for seriousness and relatedness and assess the SAR for expectedness according to Summary of Product Characteristics Nexavar® Prescribing Information (Fachinformation).

Via the safety desk, the LKP will ensure that the Ethics Committee, competent authority and participating investigators will be informed of all suspected unexpected serious adverse reactions (SUSARs) and all other relevant safety information in accordance with legal requirements.

It is the duty of the safety desk to inform the marketing authorization holder of Sorafenib according to stipulation.

Safety Desk

Studienzentrale SAL

[name]

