## 7 STUDY OUTCOME AND STATISTICAL ANALYSIS

### 7.1 Power and Sample Size Calculation, Interim Analysis

Power calculations are based on the following assumptions:

Control group:	median event free survival (EFS) 9 months
Sorafenib group:	median event free survival (EFS) 13.5 months (improvement of 50%)
Error of first kind:	$\alpha = 0.05$ (two sided)
Power:	80%
Accrual time:	24 months
Follow up:	18 months
Randomization:	1/1 allocation

To detect an improvement of median EFS from 9 months to at least 13.5 months, we need 125 evaluable patients per group i.e. a total of 250 patients to yield the necessary number of approximately 191 events.

Although all efforts will be taken to avoid patient loss to follow up, there might be a rate of loss due to various possible reasons. Censoring by transplantation in first remission will lead to an additional loss. The rate of allogeneic transplantation is assumed with about 10% of the patients. Patients receiving allogeneic stem cell transplantation will be censored for analysis at the time point of transplant. In order to account for this, exponential hazard of 0.0074 is incorporated in the sample size calculation.

Within 24 months the participating centers are able to recruit up to 300 patients fulfilling the inclusion and exclusion criteria. Taking into account a drop out rate of about 10 % the study-centers will recruit the necessary number of patients (n=276) within 24 months.

All calculations are done using SAS-Software (PROC POWER) licensed to the University of Münster.

One interim analysis and the final analysis are planned for the intent-to-treat EFS endpoint such that the overall type I error is controlled at a two-sided 0.05 level. Interim analysis will be done according to the O'Brien/Flemming approach. When 50% of the expected intent-to-treat EFS events (191 events  $\times$  0.5 = 95) are attained the first interim analysis on the intent-to-treat EFS endpoint will be conducted.

The (unblinded) interim analysis will be performed by the Studienzentrale SAL in cooperation with Institut für Medizinische Informatik und Biometrie, Münster.

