### **8.2 Monitoring**

Before the beginning of the study there will be a central meeting for all investigators from all participating centers (initiation meeting). At this meeting there will be a central training concerning all the relevant details of the study.

The National Coordinating Investigator (LKP) is responsible for data monitoring on behalf of the sponsor and has installed a central data monitoring located at the Studienzentrale SAL. During the course of the study each participating center will be visited by a monitor as often as necessary according to the number of patients enrolled. During each of these visits, source data verification will be performed on the basis of a pre-specified monitoring plan generated by the central data monitoring at the Studienzentrale SAL. Discrepancies between documented and source data will lead to queries and will have to be resolved by the investigator. Queries will be documented in a monitoring report and stored in the central data monitoring at the Studienzentrale SAL. Furthermore, at monitoring visits problematic cases as specified by the National Coordinating Investigator (LKP) will be discussed.

At the end of the study there will be a special close out visit for each center.

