### **8.3 Data Management**

The National Coordinating Investigator (LKP) is responsible for the data management on behalf of the sponsor. The LKP will make a contract for the central data management with the Koordinierungszentrum für Klinische Studien Dresden (KKS) The KKS provides a validated and certified database, which will be equipped with an audit trail which allows for a full follow-up of the history of each item.

Data capture of the study is partly paper based and partly electronically using pre-specified case report forms (CRF). The documentation of basic patient characteristics required for registration and randomization will be done by the participating investigators. The further

documentation process will be facilitated by a documentation assistant sent by the Studienzentrale SAL. Completed CRFs will be checked and paper CRFs will be collected and delivered to the Studienzentrale SAL by the monitor as soon as the requested data are available.

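### Section 8.1 has the safety committee meet with the National Coordinating Investigator and be told of significant between-arm differences, with no closed session and no limit on endpoint

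*Protocol*

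**What the plan says.** Protocol section 8.1 sets up a safety committee of three members from outside the trial. On format it says: "The committee will meet quarterly (usually by phone conference) with the National Coordinating Investigator (LKP) of the trial". The same sentence has the committee review all SAEs and SUSARs and adds that it "will be informed about statistically significant differences between the treatment arms". On action: "The Safety committee will give recommendations about the continuation of the trial and/or about necessary trial amendments". The section mentions no closed part, no coding of arms, and no endpoint, significance level or boundary.

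On blinding, section 3.3.1 says that "neither the Studienzentrale SAL nor the investigators will know which treatment arm corresponds to Sorafenib and Placebo, respectively", and promises that the blind holds for the whole trial.

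The coordinating investigator (LKP) has several operational duties:
- Section 6.2: through the safety desk at the Studienzentrale, "the National Coordinating Investigator (LKP) will review the SAE again for seriousness and relatedness".
- Section 8.2: "The National Coordinating Investigator (LKP) is responsible for data monitoring on behalf of the sponsor", with the monitoring unit located at the Studienzentrale.
- Section 8.3: "The National Coordinating Investigator (LKP) is responsible for the data management on behalf of the sponsor", with the work contracted to a coordinating centre.
- Section 9.5: the LKP writes the final report.

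On efficacy looks, section 7.1 states: "One interim analysis and the final analysis are planned for the intent-to-treat EFS endpoint". The interim is of O'Brien-Fleming type at 95 of 191 events, with overall two-sided type I error of 0.05.

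**The concern.** A committee that sees data by arm normally does so without the people who run the trial. Here the only meeting described includes the LKP, and the sentence that places the LKP there also provides for disclosing between-arm differences. In a double-blind trial, someone who judges SAE relatedness, oversees monitoring and data management, and later writes the report could then know how the arms compare while patients are still being treated and followed.

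The second issue is scope. The differences to be disclosed are not restricted to safety, and the committee advises on continuation. Section 7.1 reserves EFS comparisons for one interim and the final analysis, but nothing in section 8.1 repeats or protects that restriction.

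**Working it through.** **1. Attendance and disclosure set against blinding.** Section 8.1 describes one meeting type, with the LKP present, and one disclosure, made to the committee. It provides no other occasion for that disclosure. Section 3.3.1 keeps the Studienzentrale and the investigators unaware of which arm is sorafenib. The LKP is not named there, but is an investigator by title, and the LKP's safety desk and monitoring unit sit at the Studienzentrale. If section 8.1 is followed literally, the promise in section 3.3.1 is not secured for the LKP.

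**2. Would A/B labels be enough?** Section 3.3.1 codes the arms A and B, and only the pharmacy links the code to drug. The question is whether a safety difference reported as A against B would reveal the link. The inputs are the protocol's own tables in section 6.3.1.5: hand-foot skin reaction 30% against 7% in the renal-cell trial, and 21% against 3% in the hepatocellular trial. That similar rates occur in AML patients also receiving chemotherapy is an assumption.

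Power of a two-sided 0.05 comparison of two proportions with n per arm, where p̄ is the mean of p1 and p2:

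Φ{ [ |p1−p2|·√n − 1.96·√(2p̄(1−p̄)) ] / √(p1(1−p1)+p2(1−p2)) }

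- 30% against 7%, n = 50: (0.23 × 7.071 − 1.96 × 0.549) / 0.5245 = 0.550 / 0.5245 = 1.05, so about 85%.
- 30% against 7%, n = 69 (half of 138 per arm): (0.23 × 8.307 − 1.076) / 0.5245 = 1.59, so about 94%.
- 21% against 3%, n = 50: (0.18 × 7.071 − 1.96 × 0.4596) / 0.4416 = 0.84, so about 80%.
- 21% against 3%, n = 69: (0.18 × 8.307 − 0.901) / 0.4416 = 1.35, so about 91%.

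A reported excess of hand-foot reaction in one letter would point to sorafenib. Under these rates, even a safety-only reading of section 8.1 would probably reveal the code to anyone present by mid-accrual.

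**3. EFS, as a conditional calculation only.** The plan's own figures reproduce. Required events are 4(1.960 + 0.842)² / (ln 1.5)² = 190.97, rounded to 191, and half of that is 95.5, stated as 95. A two-look O'Brien-Fleming design has critical values of about 2.796 and 1.977. Simulating these two looks returns 5%.

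Now suppose, contrary to anything scheduled, that EFS were tested at nominal two-sided 0.05 at every quarterly meeting. A 42-month study has 42 / 3 = 14 quarters. Under no effect I take a median of 9 months in both arms, 276 patients accrued over 24 months, and a loss hazard of 0.0074 (taken as per month). Expected events are then 13.6 at month 6, 46.7 at month 12, 143.9 at month 24, 186.8 at month 30 and 228.2 at month 42. Treating the log-rank statistic as Brownian motion on that event scale (1 million simulated paths), the chance of at least one |Z| > 1.96 is:

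| Looks | Number | Chance |
|---|---|---|
| months 3 to 42 | 14 | 25% |
| months 6 to 42 | 13 | 22% |
| months 12 to 42 | 11 | 17% |

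If looks stop at month 30, the last quarter before 191 expected events, the three figures become 23%, 20% and 15%. These describe a practice that the protocol leaves open; they are not properties of the planned design.

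**The case against.** A reader might infer that EFS will be tested up to 13 times outside the single planned interim, so that the true type I error is about 22%. The documents do not support that. Section 8.1 never names EFS. The clause on significant differences closes a sentence about SAEs and SUSARs, so it may mean safety only, or it may be how the single interim result reaches the committee. Section 7.1 schedules one EFS interim. The committee only recommends, and section 8.1 contains no efficacy stopping rule. The number 13 is not stated anywhere, and it depends on when counting starts and ends. This objection stands, and no inflation is claimed for the design as planned.

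Further points can be made against the blinding concern:
- It is the committee that is to be informed. The LKP's exposure follows from attendance and is not stated. This is true, but the section offers no other setting for the disclosure.
- A/B coding hides direction. It does so only partly, given the toxicity figures above.
- Data management is contracted to a coordinating centre with an audit trail, queries come from source-data verification under a pre-specified monitoring plan, and substantial amendments need approval. These limit what the LKP could influence, so an effect on the data of all 276 patients is not shown. SAE relatedness also does not enter the EFS definition.
- Session format often sits in a committee charter, which is not at hand. A charter may well deal with this. But section 8.1 does more than stay silent: it sets attendance and disclosure, and a charter with a closed session would have to depart from it.

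**Conclusion.** The point holds for blinding. As written, section 8.1 allows the LKP to learn comparative results during the trial, which conflicts with section 3.3.1, and A/B labels would not reliably prevent it. This rests on two readings: that the LKP attends the whole of the only meeting described, and that the LKP falls under the blinding promised for investigators and the Studienzentrale. The figures of 80 to 94% for detecting a hand-foot difference at 50 to 69 patients per arm also assume that the solid-tumour rates carry over.

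For type I error the point is one of wording. Section 8.1 does not exclude EFS from the quarterly comparisons. Only if EFS were tested at nominal 0.05 at each meeting to month 42, and the result acted on, would the chance of a false-positive difference rise to roughly 17 to 25%. The protocol schedules no such testing. The change should be made because it is cheap and removes both ambiguities; the planned EFS analysis is not shown to be invalid.

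**What to change.** Amend section 8.1, and carry it into any committee charter, as follows:
- Split each quarterly meeting into an open session, with the LKP present and pooled blinded data only, and a closed session without the LKP. The closed session is for the committee and a statistician not involved in trial conduct, for example from the Münster biometry institute already named in section 7.1. Data by arm are shown only there.
- State that quarterly by-arm data are limited to safety.
- State that EFS is compared by arm only at the 95-event O'Brien-Fleming interim and at the final analysis.
- State that only the committee's recommendation, without by-arm results, passes to the LKP.

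Members and meeting schedule stay the same. The cost is a few sentences, slightly more reporting work because two sets of tables are needed, and less direct input from the LKP in the closed part. Questions to the LKP can be put in the open session.

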### ***Study specific exceptions***

Leukemia-associated serious adverse events do not have to be reported as serious adverse events on this protocol. Myelosuppression, thrombocytopenia, anemia and associated complications are expected events during leukemia therapy and are part of the treatment success (marrow emptying of leukemia cells). Therefore, myelosuppression-associated complications such as fever, infections, bleeding, and related hospitalization will be reported on appropriate pages of the CRF as an adverse event. In this context only prolonged myelosuppression, i.e. pancytopenia with marrow hypocellularity on day 40 or later from start of last cytotoxic therapy without evidence of leukemia, will require immediate reporting on an SAE form.

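### Section 8.1 lets significant arm differences reach the safety committee every quarter, alongside the coordinating investigator and with no limit to safety, and its stated review omits non-fatal myelosuppression-associated infections and bleeding

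*Protocol*

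**What the plan says.** **Efficacy looks (section 7.1).** "One interim analysis and the final analysis are planned for the intent-to-treat EFS endpoint", and these are set up so that the "overall type I error is controlled at a two-sided 0.05 level". The interim falls at 95 of 191 events: "Interim analysis will be done according to the O'Brien/Flemming approach". No numerical bound is given.

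**Safety committee (section 8.1).** "The committee will meet quarterly (usually by phone conference) with the National Coordinating Investigator (LKP) of the trial". It reviews all SAEs and SUSARs, "will be informed about statistically significant differences between the treatment arms", and recommends on continuation or amendment. The section does not say which endpoints are compared, at what level, or whether the LKP leaves for any part of the meeting.

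**The LKP's other duties.** "The National Coordinating Investigator (LKP) is responsible for central safety monitoring and reporting on behalf of the sponsor" (section 6.2), which includes a second review of each SAE for seriousness and relatedness. The LKP is also responsible for data monitoring (8.2) and for data management, which is contracted out (8.3).

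**Blinding (section 3.3.1).** Neither the central study office nor the investigators are to know which coded arm is Sorafenib, and the blind is guaranteed for the whole trial.

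**SAE exceptions (section 6.1, Study specific exceptions).** Here "myelosuppression-associated complications such as fever, infections, bleeding, and related hospitalization will be reported on appropriate pages of the CRF", as adverse events. In that context only prolonged myelosuppression needs an SAE form. Section 6.1 also puts every death on treatment, and for 30 days after it, on an SAE form.

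**The concern.** Three weaknesses meet in one paragraph of section 8.1.

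1. **Type I error.** A committee that can recommend stopping, hears of significant differences every quarter and is not told which endpoints these concern has a route to efficacy looks outside the O'Brien-Fleming plan. The 0.05 claim in 7.1 depends on that route staying unused, and nothing in 8.1 closes it.
2. **Interim knowledge.** The LKP sits in the meeting where differences are reported. Learning that a difference has appeared, or that none has, gives comparative information to someone who judges SAE relatedness, directs monitoring and is responsible for the data.
3. **Safety coverage.** Section 2.2 names added treatment-related toxicity as the trial's main risk. Section 6.3.1.2 names bleeding as a Sorafenib risk, and 6.3.1.5 reports febrile neutropenia, sometimes fatal, in combination with cytotoxic drugs. In induction the study drug runs from day 10 to day 19, after chemotherapy that starts on day 1 (4.3.2), so it falls in the period of expected myelosuppression. A non-fatal severe infection or bleed in that period lies outside the committee's SAE and SUSAR review.

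**Working it through.** **Reproducing the plan's figures.** Inputs from section 7.1: medians 9 and 13.5 months, two-sided α 0.05, power 80%, accrual 24 months, follow-up 18 months, censoring hazard 0.0074 (taken as monthly).

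- Schoenfeld events: HR = 9/13.5 = 0.667; d = 4 × (1.960 + 0.842)² / (ln 0.667)² = 4 × 7.85 / 0.1644 ≈ 191. This matches.
- Expected events from 250 patients with exponential EFS and uniform accrual: event probabilities 0.8268 and 0.7113, so 125 × (0.8268 + 0.7113) = 192.3. This matches.

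**The planned two-look design.** Solving for the O'Brien-Fleming constant at information 0.5 and 1 with overall two-sided error 0.05 gives c = 1.977.

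- Interim: |Z| ≥ 1.977 × √2 = 2.797, p = 0.0052.
- Final: |Z| ≥ 1.977, p = 0.0480.

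With only these two looks, type I error is 0.05 as claimed.

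**What extra EFS looks would do.** This is a what-if; section 8.1 does not say that EFS is tested quarterly. Assumptions: no effect, median 9 months in both arms (λ = ln 2 / 9 = 0.0770 per month), η = 0.0074, 276 patients accrued uniformly over 24 months, meetings every 3 months to month 42 (14 meetings), each using |Z| > 1.96, and a significant result acted on. Expected events at time t:

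E(t) = (276/24) ∫₀^min(t,24) [λ/(λ+η)] [1 − exp(−(λ+η)(t−s))] ds

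This gives 4, 14, 28, 47, 68, 92, 117, 144, 168, 187, 201, 213, 221 and 228 events. The log-rank score process was simulated as Brownian motion on these counts (400,000 runs):

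| Looks counted | Number | Chance of at least one significant result |
|---|---|---|
| All quarters | 14 | 0.25 |
| From 10 events on | 13 | 0.22 |
| From 20 events on | 12 | 0.19 |
| From 40 events on | 11 | 0.17 |
| Five early looks (14 to 92 events), then O'Brien-Fleming at 95 and 191 | 7 | 0.18 |

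The 14-look figure counts a look at about 4 events, where the normal approximation is poor, so the rows below it are more realistic. Several rows also run past the 191 events of the final analysis. In the same simulation without looks beyond 191 events, the result is about 0.20 for looks from 10 events on (nine looks) and 0.15 for looks from 40 events on (seven looks). One unadjusted look at half information plus an unadjusted final would give 0.083.

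**If the comparisons are safety-only, or simply relay the planned interim,** no EFS look is added and type I error stays at 0.05.

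**Safety coverage, side by side.**

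| Event | Reaches the committee's SAE/SUSAR review? |
|---|---|
| Death on treatment or within 30 days after it | Yes (6.1) |
| Prolonged myelosuppression | Yes (6.1) |
| Serious infection or bleed not associated with myelosuppression | Yes |
| Non-fatal infection, bleed or related hospitalization associated with myelosuppression | No; CRF adverse event only |

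**The case against.** The best defence is that section 8.1 describes a safety committee. Read with 7.1, which fixes the efficacy analyses, its sentence on significant differences can mean safety comparisons, or the planned interim being passed on. No quarterly EFS test, nominal level or stopping rule is written down, and the committee only recommends. This stands: a reader might infer that the 0.05 level is already broken, and the text does not support that. The 0.17 to 0.25 range describes one permitted reading.

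A reader might also infer that the blind is broken. Section 8.1 informs the committee, names no drug and opens no patient code, and arms are coded A and B with the key held at the pharmacy. The exposure is to comparative results, through the LKP's presence, and not to individual allocations. A DSMB charter, if there is one, may provide a closed session. Even so, the attendance that the protocol itself fixes is with the LKP.

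Two readings on safety go too far. The committee reviews all SAEs, so significance is no filter on that review; being told of significant differences is an additional item. Nor are infections and bleeding in general removed from SAE reporting, as the table above shows. What remains is that the non-fatal myelosuppression-associated events have no stated route to the committee except through a significant difference, which is a weak trigger while events are few.

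Section 7.1 also has the central study office take part in the unblinded interim, which conflicts more directly with 3.3.1. That needs its own correction.

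**Conclusion.** The concern holds as a conditional weakness, not as a proven loss of type I error control or of the blind. Section 8.1 leaves the claim in 7.1 unprotected. The error on EFS is 0.05 if the quarterly comparisons are confined to safety, and about 0.17 to 0.25 if EFS is tested at nominal 0.05 each quarter and acted on, under the accrual, hazard and look-timing assumptions listed above. The LKP's attendance works against the purpose of the blinding guarantee in 3.3.1 whichever endpoints are compared. The gap in safety review is narrower than infections and bleeding as a whole, but it covers harms that the protocol itself associates with Sorafenib, at a time when they are likely.

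**What to change.** Amend section 8.1, and the DSMB charter if there is one:

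1. By-arm efficacy results go to the committee only at the planned 95-event interim, judged against the O'Brien-Fleming bound (about p < 0.005, which should be stated).
2. By-arm material is reviewed in a closed session without the LKP, who attends an open session with pooled data only.
3. The quarterly report adds a descriptive by-arm table of deaths and of grade 3 or higher infections and bleeding, taken from the CRF adverse event pages and supplied whether or not any difference is significant.

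The cost is a few sentences and one extra quarterly table. The events are already recorded and graded under section 6.2, so no new data are collected. The practical demand is that someone outside the blinded team must prepare the table.
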